*Clinical relevance of genetic risk information.* One potentially important clinical application of genetic testing for lung cancer risk is the provision of test feedback to smokers in the hopes of encouraging cessation. Accumulating research in this area has yielded mixed results, with recent meta-analyses suggesting that genetic feedback about increased lung cancer risk can result in significant short-term improvements in smoking cessation, but no long-term changes. These findings are perhaps not surprising, given the poor long-term smoking cessation success rates, even with available treatments. Experimental studies that systematically manipulate risk information and assess immediate outcomes that are relevant to behaviour change (e.g., worry, perceived risk, motivation to quit) might provide a clearer and more accurate picture of the utility of genetic testing feedback in presenting a “teachable moment” in which to intervene to encourage behaviour change. Consistent with this possibility, Consultant [name] and colleagues conducted an experimental study in which hypothetical lung cancer genetic risk information was manipulated, and they found that high-risk information caused immediate increases in motivation to quit smoking. Our pilot data from AA current smokers also confirms this. Similarly, other experimental studies using hypothetical risk information as a model found that genetic risk feedback resulted in immediate increases in worry and perceived risk. Overall, the literature suggests that experimental studies of hypothetical risk can be a useful tool in understanding the short-term effects of receiving genetic risk information. What has not yet been examined is the possibility that adding personally relevant information to the feedback can enhance effects. Feedback regarding genetic ancestry may thus also have a significant impact on perceived risk, worry, and motivation to quit. Based on empirical and theoretical models of health literacy and numeracy advanced by Consultant [name] and others, the proposed study will explore the potentially important contribution of personally relevant quantitative information to key motivational outcomes related to behaviour change. For example, AA smokers who are informed that their genetic ancestry is in fact highly concordant with AA heritage may be particularly concerned about genetic risks that have been shown to be overrepresented in AAs. Conversely, those who learn that they have low levels of genetic concordance with AA heritage may then self-identify less strongly as AA, resulting in lower concern for genetic risks that are overrepresented in AA smokers. To date, no study has investigated this intriguing possibility.

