**Aim 3:** Variance stabilizing and normalizing transformations will be applied to the data as appropriate. Analysis of variance will be used to identify the individual and interaction effects of factors on each outcome measure. The Benjamini-Hochberg FDR method will be used to adjust for multiple tests involving each factor or interaction across the various outcome measures, and each test with an FDR  $\leq 10\%$  will be considered significant. The primary study analyses will be a 2 (Risk) x 2 (Ancestry) factorial ANOVA. With this statistical approach, we will be able to test for main effects of Risk and Ancestry, as well as Risk x Ancestry interactions. The primary outcome measure will be motivation to quit; perceived risk, cancer worry, and psychological distress will serve as secondary outcomes. In addition to this primary analysis, we will also consider including covariates (e.g., demographics, numeracy, FTND, study site, gender, age) to control for external sources of variation. Finally, we will be able to explore possible moderating effects of these covariates. Although of course, the proposed study is not powered to detect such effects, such exploratory findings may be important when deciding next steps in formally utilizing the results to develop interventions aimed at increasing knowledge of genetic lung cancer risk.

**Sample size and power:** Power computations for this aim are based on the 2 x 2 factorial design described above. With 90 participants per experimental condition (combination of genetic risk and ancestry), we would be able to detect an effect size of 0.685 due to genetic risk or ancestry at a significance level of 0.0125 with 80% power. Similarly, we would be able to detect an effect size of 0.895 due to an interaction between genetic risk and ancestry at a significance level of 0.0125 with 80% power. A significance level of 0.0125 has been used to account for the four outcome measures of interest in this aim and the calculations are based on a standard deviation of 1.37 for motivation to quit smoking from the literature.

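### Aim 3 gives its only primary outcome no significance level of its own, and its power statement does not follow from the 2 x 2 design

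*Combined protocol and SAP*

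**What the plan says.** All of this is in section 13.0, Aim 3, unless noted.

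- **Outcomes:** "The primary outcome measure will be motivation to quit; perceived risk, cancer worry, and psychological distress will serve as secondary outcomes".
- **Tests:** a 2 x 2 ANOVA is to "test for main effects of Risk and Ancestry, as well as Risk x Ancestry interactions".
- **Significance rule:** BH "will be used to adjust for multiple tests involving each factor or interaction across the various outcome measures", with an FDR of 10% or less counted as significant. No sentence tests motivation first, separately or at its own level.
- **Power:** with 90 participants per condition, SD 1.37 and 80% power, the plan claims to detect 0.685 for either main effect and to "detect an effect size of 0.895 due to an interaction between genetic risk and ancestry at a significance level of 0.0125". The level is explained thus: "A significance level of 0.0125 has been used to account for the four outcome measures of interest in this aim".
- **Sidedness:** stated as two-sided for Aims 1 and 2, not stated for Aim 3.
- **Expected effects (section 3.0):** earlier experiments found that "genetic risk feedback resulted in immediate increases in worry and perceived risk" and that "high-risk information caused immediate increases in motivation to quit smoking". Ancestry feedback "may thus also have a significant impact on perceived risk, worry, and motivation to quit".
- **Status (section 2.0):** Aim 3 is worded as exploratory and lists the four outcomes side by side.

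**The concern.** Naming one primary outcome normally means that its verdict rests on its own data at a level fixed in advance. Here the label has no effect on inference. BH limits the expected share of false findings across a family and does not fix the error rate on one named member. The same motivation p-value can therefore be significant or not because of worry, perceived risk or distress. Section 3.0 expects at least worry and perceived risk to respond to risk feedback, so the looser cut-offs are realistic.

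The power statement should tell the reader what the primary analysis can detect. It uses a Bonferroni split (0.05/4 = 0.0125) that the analysis does not apply. Its two detectable effects also do not seem to come from the same design or the same kind of test. If so, the reader cannot tell what Aim 3 is powered for.

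**Working it through.** **1. BH cut-offs.** There are four outcomes per effect and q = 0.10. The k-th step is 0.10 x k/4, giving 0.025, 0.05, 0.075 and 0.10. With all three secondary p-values at 0.9, motivation needs p of 0.025 or less. With one, two or three of them at 0.001, it needs 0.05, 0.075 or 0.10. If the sentence instead means one pooled family of 12 tests, the steps are 0.10 x k/12, from 0.0083 to 0.10.

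**2. Size of the effect.** This comes from simulating four two-sided z-tests per effect, with motivation unaffected. Two inputs are assumed because the documents do not give them: correlations between outcomes of 0 to 0.5, and noncentralities of 3 to 5 for responding secondaries. The family is four tests per effect.

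| Secondaries responding | False-positive rate for motivation, per effect |
|---|---|
| none | 2.9-3.7% |
| one | 5.0-5.9% |
| two | 6.9-8.0% |
| three | 8.7-10.0% |

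A motivation p of 0.06 is called significant in 2-11% of cases with no responder and in 75-100% with two. BH and a fixed 0.05 reach different verdicts on an unaffected motivation score in about 2-3% of trials with none or two responding, and in up to 5.0% with three. With exactly one responder the BH cut-off is itself close to 0.05 and the rules nearly agree. If motivation has a true main effect of 0.406 they differ in 4-8% of trials (none or two responders); at 0.685, in 0.3% or fewer.

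**3. The plan's main-effect figure.** Inputs: SD 1.37, 90 per cell (360 in total), level 0.0125. I read the effect size as a difference in scale points; 0.685 is 0.5 x 1.37.

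- *Reproducing 80%:* for 90 v 90, SE = 1.37 x sqrt(2/90) = 0.2042 and 0.685/0.2042 = 3.354. The two-sided 0.0125 critical value is 2.498, so power = Phi(0.856) = 80.4% (80.0% by noncentral F). That is 180 participants: two single cells, or 45 per cell.
- *The factorial contrast:* a main effect compares 180 with 180. SE = 1.37 x sqrt(2/180) = 0.1444 and 0.685/0.1444 = 4.743. Power = Phi(2.246) = 98.8% (98.7% by noncentral F, 356 df).

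**4. The plan's interaction figure.** As a difference of differences, SE = 1.37 x sqrt(4/90) = 0.2888 and 0.895/0.2888 = 3.099.

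- Two-sided 0.0125: Phi(3.099 - 2.498) = 72.6% (72.2% by noncentral F).
- One-sided 0.0125 (critical value 2.241): Phi(0.858) = 80.4%.

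**5. Is there a common basis?** The first figure needs a two-sided test on half the sample. The second needs a one-sided test on the whole sample. One-sided, 0.685 has 99.4% power for 180 v 180, and Phi(3.354 - 2.241) = 86.7% for 90 v 90. No single sidedness gives 80% for both.

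**6. Detectable differences at 80% power** (noncentral F, 356 df, SD 1.37, 90 per cell, two-sided):

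| Level | Main effect (180 v 180) | Interaction |
|---|---|---|
| 0.0125 | 0.484 | 0.969 |
| 0.025 | 0.447 | 0.894 |
| 0.05 | 0.406 | 0.811 |

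**The case against.** **The BH rule is a legitimate choice.** It is pre-specified, consistent with the outcome list, and controls what it claims to control. For an aim worded as exploratory across four outcomes, an FDR family is coherent. This stands. A reader might infer that the rule contradicts the primary label or makes the analysis invalid; the documents do not support that.

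**The inflation needs an unusual pattern.** Motivation must be unaffected while secondaries respond, yet section 3.0 expects motivation itself to respond. This also stands. A reader might infer a 10% error rate on the primary outcome, or 27% over the three effects (1 - 0.9^3). The latter needs all three secondaries to respond to Risk, Ancestry and the interaction, which the documents do not predict. Under the pooled reading of 12 tests, the per-effect rate stayed below 5% in the settings examined.

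**A fixed 0.05 is not better everywhere.** With no responders it is looser than BH. If motivation truly responds (0.406) together with two secondaries, BH has about 83-85% power against 80%. Applied to all three effects without adjustment, 0.05 gives 1 - 0.95^3 = 14.3% for at least one false positive. BH gives 8.4-10.7% with no responders, 12.5-14.6% with two responding to Risk only, and 16.4-18.4% with two responding to both factors. This is why the change to the testing rule is only optional and limited to one effect.

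**Sizing at 0.0125 is conservative.** It lies below every cut-off in a family of four, though not below 0.0083 in a pooled family. That does not explain the two power figures. Sidedness is unstated, so the 72.2% is conditional on a two-sided test, but a one-sided test moves the main-effect figure further from 80%.

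**Conclusion.** Two conclusions, of different weight.

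The power statement is wrong as written. With 90 per cell the main effects are better powered than claimed (98.7% for 0.685). The interaction is less well powered at two-sided 0.0125 (72.2% for 0.895). A reader might infer that Aim 3 is too small; that does not follow, since at two-sided 0.05 the interaction of 0.895 has 87.1% power. This conclusion rests on the plan's SD and cell size, equal cells, and effect sizes in scale points. If they were meant in SD units, the 80% values at two-sided 0.0125 would be 0.484/1.37 = 0.353 and 0.969/1.37 = 0.707, which match neither figure.

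The lack of a level for the primary outcome is real but modest. The moving cut-off is exact arithmetic: 0.025 to 0.10 for families of four, 0.0083 to 0.10 if pooled. The error rates depend on the assumed correlations and responses. The rule matters only for a motivation p-value inside that range.

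**What to change.** 1. **Restate the power statement (needed).** Define the main effect as 180 v 180 and the interaction as a difference of differences, state the sidedness, and say how the chosen level relates to the planned test. At 80% power the detectable differences are 0.484 and 0.969 at two-sided 0.0125, or 0.406 and 0.811 at two-sided 0.05.

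2. **State the BH family (needed for clarity).** Say whether there are three families of four or one of 12.

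3. **Give the primary outcome its own test (optional).** Name the one factorial effect on motivation to quit that carries the primary claim. Test it at a fixed two-sided 0.05 outside the BH family, and quote its power at that level. Keep BH at 10% for the secondary outcomes and the remaining effects. Do not treat all three effects as primary at an unadjusted 0.05, because of the 14.3% above.

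The cost is a few sentences in section 13.0 and no extra participants. The third change has two downsides: a p-value between 0.05 and 0.10 for the named effect no longer counts, and 0.05 is looser than BH when no secondary responds.

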## 2.0 Objectives

Aim 1: Identify ancestry-informative variants in tobacco metabolism and detoxification pathway genes that correlate with metabolic/detoxification capacity in AA smokers.

Aim 2: Identify ancestry-informative variants in tobacco addiction pathway genes that correlate with measures of nicotine dependence in AA smokers.

Aim 3: Explore the possibility that genetic feedback about increased lung cancer risk associated with African American ancestry may influence perceived risk, cancer worry, acute psychological distress, and motivation to quit.

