For Aim 3: Participants recruited through Aims 1 and 2 at each of the two study sites will be randomly assigned to one of four conditions, in a 2 x 2 fully-crossed between-groups factorial design. In one group ("High Risk, High Ancestry [HRHA]"), participants will be asked to consider a hypothetical scenario in which genetic test results reveal that: 1) they carry genotypes that place AA smokers at a particularly high (~50%-80%) risk for the development of lung cancer, and 2) their profile of AIMs reflects a particularly high concordance with AA heritage (~90%). In a second group ("Low Risk, Low Ancestry [LRLA]"), participants will be asked to consider a scenario in which genetic test results reveal that: 1) they are at normal (~7%-10%) risk for the development of lung cancer, and 2) their profile of AIMs reflects a particularly low concordance with AA heritage (~10%). The final two groups will receive "High Risk, Low Ancestry (HRLA)" and "Low Risk, High Ancestry (LRHA)" hypotheticals, respectively. Participants will be block randomized by age and gender to one of four groups following the 2 (Risk) x 2 (Ancestry) design. To increase feasibility, randomization will be conducted independently at all sites. Following randomization, participants will be presented with a brochure describing the nature of two hypothetical genetic tests, one which assesses lifetime risk for the development of lung cancer in AA smokers, and one which characterizes the degree of a participant's genetic concordance with AA ancestry. The brochure will be explained in a standardized fashion to the participants by the graduate student trainees. Participants will then be given the hypothetical feedback according to their randomized condition (HRHA, HRLA, LRHA, LRLA), followed immediately by the post-feedback assessments (see Measures). Participants will then be debriefed, offered a \$30 gift card, and thanked for their participation.

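### Aim 3 randomises by age, gender and site, but its primary 2 x 2 ANOVA leaves these factors out and forgoes a small, almost free gain in power

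*Combined protocol and SAP*

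**What the plan says.** Section 4.1 describes the Aim 3 allocation: "Participants will be block randomized by age and gender to one of four groups following the 2 (Risk) x 2 (Ancestry) design". It then adds: "To increase feasibility, randomization will be conducted independently at all sites". Age, gender and site are therefore all factors of the randomisation.

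Section 13.0, Aim 3, names the primary model: "The primary study analyses will be a 2 (Risk) x 2 (Ancestry) factorial ANOVA". Its terms are Risk, Ancestry and their interaction, and motivation to quit is the primary outcome. The randomisation factors come up only afterwards: "In addition to this primary analysis, we will also consider including covariates (e.g., demographics, numeracy, FTND, study site, gender, age". No other section makes them required terms.

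Two thresholds are in play. The decision rule is Benjamini-Hochberg (BH), which "will be used to adjust for multiple tests involving each factor or interaction across the various outcome measures, and each test with an FDR" of at most 10% is called significant. The sample-size paragraph instead uses a fixed level: "A significance level of 0.0125 has been used to account for the four outcome measures of interest in this aim". Section 2.0 words the aim as exploratory: "Explore the possibility that genetic feedback about increased lung cancer risk associated with African American ancestry may influence perceived risk".

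**The concern.** Blocked allocation makes the four arms alike in age, gender and site. If those factors predict the outcome, the arm means vary less than they would under simple randomisation. An ANOVA without the factors does not see this: it leaves their variance in the residual, so its standard errors are too large. Tests reject too seldom under the null and have less power than a model containing the factors.

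What is at stake is mostly the Risk x Ancestry interaction, where power is tightest. There is also a question of prespecification. The covariate list is open-ended and its use is optional, so the adjusted model could be chosen after the results are known. Aims 1 and 2 adjust outright for age and recruitment setting; Aim 3, the only randomised aim, does not.

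**Working it through.** **Inputs from Section 13.0, Aim 3:** 90 per condition (N = 360), SD 1.37, main effect 0.685, interaction 0.895, level 0.0125, BH at 10% over four outcomes. Two-sided tests are assumed, as in Aims 1 and 2.

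**Assumed, because the documents do not give it:** R2, the share of outcome variance explained by age, gender and site, from 0 to 20%.

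**1. The plan's own figures.** Comparing 90 with 90, SE = 1.37 x sqrt(2/90) = 0.204. At 0.0125 an effect of 0.685 then has 80% power, so the stated figure reproduces as a comparison of two single cells. A factorial main effect compares 180 with 180: SE = 2 x 1.37/sqrt(360) = 0.1444, and power at 0.685 is 98.7%. The interaction, read as a difference of differences, has SE = 4 x 1.37/sqrt(360) = 0.2888. At 0.895 its power is 72.2% at 0.0125 and 80.1% at 0.025. So 0.895 does not reproduce at the stated level. That is a separate matter, not caused by the missing terms.

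**2. Effect of adjustment.** With balanced blocking the true SE is SE x sqrt(1 - R2). The unadjusted test uses SE with 360 - 4 = 356 df. The adjusted test uses SE x sqrt(1 - R2) with 352 df (1 for gender, 2 for three age bands, 1 for two sites; band and site counts assumed).

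Example at R2 = 10% and cut-off 0.025 (critical t 2.251): the true SE is 0.2888 x sqrt(0.9) = 0.2740.
- Unadjusted: the estimate must exceed 2.251 x 0.2888 = 0.650. (0.895 - 0.650)/0.2740 = 0.894, so power is 81.4%.
- Adjusted: it must exceed 2.251 x 0.2740 = 0.617. (0.895 - 0.617)/0.2740 = 1.015, so power is 84.5%.

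**3. Interaction power at 0.895, unadjusted vs adjusted (%), noncentral t.** BH at 10% over four outcomes implies cut-offs of 0.025, 0.05, 0.075 and 0.10 by rank. The 0.0125 row is the sample-size level, shown for reference only.

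| Cut-off | R2 = 0 | 2% | 5% | 10% | 20% |
|---|---|---|---|---|---|
| 0.025 | 80.1 / 80.1 | 80.4 / 81.0 | 80.7 / 82.3 | 81.4 / 84.5 | 82.8 / 88.7 |
| 0.05 | 87.1 / 87.1 | 87.3 / 87.7 | 87.7 / 88.7 | 88.3 / 90.3 | 89.7 / 93.3 |
| 0.10 | 92.6 / 92.6 | 92.8 / 93.0 | 93.1 / 93.7 | 93.7 / 94.7 | 94.7 / 96.5 |
| 0.0125 | 72.2 / 72.2 | 72.4 / 73.2 | 72.7 / 74.8 | 73.2 / 77.5 | 74.4 / 82.9 |

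**4. Full BH rule, simulated for motivation to quit.** Assumed: permuted blocks of 4 in 12 strata (2 sites x 2 genders x 3 age bands), equal R2 on all four outcomes, residual correlation 0.4; 16,000 trials per power figure.

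| Outcomes with the interaction | R2 = 0 | 2% | 5% | 10% | 20% |
|---|---|---|---|---|---|
| Motivation to quit only | 81.4 / 81.3 | 81.6 / 82.2 | 81.8 / 83.6 | 82.3 / 85.7 | 83.3 / 89.6 |
| All four | 91.3 / 91.3 | 91.5 / 91.8 | 91.8 / 92.6 | 92.5 / 93.8 | 93.6 / 96.0 |

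With residual correlation 0 (6,000 trials) and R2 = 10%, the pairs are 82.9 / 86.0 and 93.0 / 94.3.

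**5. Under the null.** With no true interaction, the realised FDR against the 10% target at R2 of 0, 10 and 20% is 8.8, 7.2 and 5.4% unadjusted, and 8.9, 9.6 and 9.7% adjusted (8,000 trials each). The unadjusted test is conservative, not invalid.

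**6. Main effects.** At 0.685, power is at least 98.7% at 0.0125, and at least 99.3% at 0.025 or above, for both models and every R2. A smaller main effect would gain more: at 0.482, level 0.0125 and R2 = 10%, simulated power is 81.2 vs 84.9%.

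**The case against.** Nothing the plan promises is lost. The unadjusted ANOVA is valid after stratified randomisation, and at the BH cut-offs its interaction power at 0.895 is 80.1% or more for every R2. The benefit rests on an R2 the documents do not give and may be nil; the 20% column has no support in the text. The plan already names site, gender and age as covariates, and an unadjusted primary analysis with an adjusted secondary one is defensible in an exploratory aim. The primary model is itself fixed, so the open wording leaves only the additional analysis free. The mismatch between 0.895 and its stated level matters more for the power statement.

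All of this is fair as to weight, and it keeps the point minor. It does not remove it. The primary analysis still ignores the factors used to randomise, adjusting costs essentially nothing at R2 = 0, and the choice of adjusted model remains open until it is written down.

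**Conclusion.** The point holds as a small, low-cost improvement. The primary Aim 3 model omits the factors by which the trial randomises. Type I error is not inflated, and unadjusted power does not fall below its R2 = 0 value. What is forgone under the BH rule is interaction power: about 1 to 3.5 points at R2 = 10%, about 0.5 to 2 at 5%, under 1 at 2% or less, and nothing at 0. This rests on the assumed R2, on reading 0.895 as a difference of differences, on SD 1.37, and on the assumed strata, block size and outcome correlation in the simulation. Confidence in the direction is high; confidence in the size is limited by the unknown R2.

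**What to change.** In Section 13.0, Aim 3, define the primary model as Risk, Ancestry, Risk x Ancestry, age, gender and randomising site, and fix it before the data are seen. Two definitions are needed:
- **Age:** state whether it enters in its blocking bands (which Section 4.1 does not give) or as a continuous term.
- **Site:** define it as the unit that keeps its own randomisation list. Section 4.0 lists three centres, while Section 4.1 refers both to two study sites and to all sites.

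Keep the BH rule as planned, and report the unadjusted 2 x 2 ANOVA as a sensitivity analysis. The cost is SAP wording and about 4 of 356 residual degrees of freedom. All three factors are known at randomisation, so no new data are needed.

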**Aim 2:** For each SNP, nicotine dependence (as determined by high-very high FTND scores: 6-10) will be modeled using genotype after adjusting for smoking dose (pack-years), age and recruitment setting using logistic regression (LR). Sensitivity, specificity and prediction accuracy (along with 95% confidence bounds) will be used to characterize the precision of binary predictions from LR. Multiple linear regression will be used to correlate the proportion of African ancestry with FTND score (low vs. high) after adjusting for smoking dose, age and recruitment setting. All tests will be two-sided and the Benjamini-Hochberg method will be used to account for multiple testing. Secondary outcomes will include cigarettes per day, age at initiation, and intention to quit. To account for the potentially large number of SNPs resulting from this univariate analysis, penalized logistic regression (PLR) will be used to develop a prediction model for nicotine dependence using these SNPs. PLR has been demonstrated to have excellent power to identify covariate effects as well as superior prediction accuracy compared to competing methods like Classification and Regression Trees and Multifactor Dimensionality Reduction. Sensitivity, specificity and prediction accuracy (along with 95% confidence bounds) will be used to characterize the precision of binary predictions from PLR. AUC curves (along with 95% confidence bounds) will be used to characterize the predictive value of models from these methods. A participant whose predictive probability is  $> 0.5$  will be classified as having high nicotine dependence; however, alternative thresholds will also be evaluated in this

analysis. In addition, the performance of each model will be evaluated using leave-one-out cross validation. All computations will be performed using R statistical language and environment.

**Sample Size and Power:** With 180 subjects each in the low-medium (scores 0-5) and high-very high (scores 6-10) nicotine dependence groups, we will have 80% power to detect a difference in the range of 0.14-0.19 (in minor allele frequency between groups in SNPs of interest) at the 0.005 significance level. This calculation assumes a 10-40% minor allele frequency in the low nicotine dependence group.

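### Aim 3: the detectable effects of 0.685 (main effect) and 0.895 (interaction) do not follow from one definition of effect at alpha 0.0125, and the interaction effect is not defined

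*Combined protocol and SAP*

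**What the plan says.** Section 13.0 (Statistical Analysis), Aim 3, plans a 2 x 2 factorial ANOVA with which "we will be able to test for main effects of Risk and Ancestry, as well as Risk x Ancestry interactions". The sample size paragraph that follows states:

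- Basis: "Power computations for this aim are based on the 2 x 2 factorial design described above".
- Cell size: "With 90 participants per experimental condition (combination of genetic risk and ancestry").
- Main effects: the trial can "detect an effect size of 0.685 due to genetic risk or ancestry at a significance level of 0.0125 with 80% power".
- Interaction: it can "detect an effect size of 0.895 due to an interaction between genetic risk and ancestry at a significance level of 0.0125 with 80% power". A design-of-experiments textbook (reference 42) is cited here.
- Variability: "the calculations are based on a standard deviation of 1.37 for motivation to quit smoking from the literature". The alpha of 0.0125 allows for four outcome measures.

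The paragraph gives no formula, does not define the interaction effect in terms of cell means, and does not say whether the Aim 3 tests are one- or two-sided. For Aim 2 the same section says: "All tests will be two-sided and the Benjamini-Hochberg method will be used to account for multiple testing". Aim 1 is also two-sided. For Aim 3, significance will be judged by Benjamini-Hochberg at a 10% false discovery rate across the outcome measures. Section 2.0 words the aim as exploratory: "Explore the possibility that genetic feedback about increased lung cancer risk".

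**The concern.** Both figures are given for the same trial, cell size, SD, alpha and power. In a balanced 2 x 2 design each main effect and the interaction is a one-degree-of-freedom contrast. At common alpha and power, the ratio of two detectable effects is therefore fixed by how the contrasts are defined; the SD and cell size cancel. The printed ratio of 0.895 to 0.685 matches none of the usual definitions.

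The consequence is mainly one of interpretation. A reader faced with a null Risk x Ancestry result needs to know what size of interaction the trial could have found. The interaction matters here because the background section argues that ancestry feedback may change how smokers respond to genetic risk information. As printed, the reader cannot tell whether 0.895 is optimistic or very conservative.

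**Working it through.** **Inputs**

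| Input | Value | Source |
|---|---|---|
| Participants per cell | 90 (360 in total) | Section 13.0, Aim 3; section 4.0 |
| SD, motivation to quit | 1.37 | Section 13.0, Aim 3 |
| Alpha | 0.0125 | Section 13.0, Aim 3 |
| Power | 80% | Section 13.0, Aim 3 |
| Sidedness | two-sided | Assumption: stated for Aims 1 and 2, and the ANOVA F test is non-directional |
| Error df | 360 - 4 = 356 | Follows from the 2 x 2 ANOVA |

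Effects are read in raw scale points, since an SD is supplied.

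**Formula.** For a one-df contrast, SE = 1.37 x sqrt(c/90), where c depends on the contrast. For F(1, 356) at alpha 0.0125, 80% power needs a noncentrality of 11.25, so the detectable effect is SE x sqrt(11.25) = SE x 3.354.

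| Contrast | c | SE | Detectable effect | In SDs |
|---|---|---|---|---|
| Main effect, 180 v 180 | 1 | 0.1444 | 0.484 | 0.35 |
| One cell v one cell, 90 v 90 | 2 | 0.2042 | 0.685 | 0.50 |
| Interaction, difference of differences | 4 | 0.2888 | 0.969 | 0.71 |
| Interaction, half the difference of differences | 1 | 0.1444 | 0.484 | 0.35 |

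**The 0.685 figure.** It is reproduced exactly, but as a comparison of two single cells. Solving for c gives (0.685/1.37)² x 90/11.25 = 2.00. This supports the reading of n, SD, alpha and units. It is not the main effect that the ANOVA tests. For that contrast the noncentrality is (0.685/0.1444)² = 22.5 and power is 98.7%.

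**The 0.895 figure.** Solving for c gives (0.895/1.37)² x 90/11.25 = 3.41, which is not 1, 2 or 4. Power at two-sided 0.0125:

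- as a difference of differences: noncentrality (0.895/0.2888)² = 9.60, power 72.2%;
- with the cell-versus-cell variance (c = 2): noncentrality 19.2, power 96.9%;
- as half the difference of differences: noncentrality 38.4, power 99.99%.

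**The ratio.** 0.895/0.685 = 1.307, or 1.305 to 1.308 allowing for rounding of both figures. The contrasts above allow 2 (difference of differences v main effect), sqrt(2) = 1.414 (difference of differences v cell-versus-cell) or 1 (half contrast v main effect).

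**Other readings tried**

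- Numerator df of 2: main effect 0.530, cell-versus-cell 0.750, difference of differences 1.060. Numerator df of 3: 0.561, 0.793 and 1.121. Neither set contains the printed pair.
- Effects read in SD units: 0.685 has 77% to over 99.9% power and 0.895 has 96% to over 99.9%, depending on the contrast; none gives 80%.
- One-sided 0.0125 (equivalent to two-sided 0.025): the difference of differences is detectable at 0.894, and 0.895 has 80.1% power. On that basis 0.685 has about 86% power (90 v 90) or 99.4% (180 v 180).

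**Simulation check** (200,000 draws, two-sided 0.0125): power 0.720 for a difference of differences of 0.895, 0.799 for 0.969, 0.987 for a main effect of 0.685, and 0.798 for 0.484.

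**The case against.** The strongest reply is that 0.0125 is not the threshold the analysis will use. Benjamini-Hochberg at 10% across four outcomes rejects any test with p at or below 0.10/4 = 0.025. At two-sided 0.025 a difference of differences of 0.895 has 80.1% power, so on that reading the planned test delivers what the paragraph promises. This stands as a statement about practical consequence, and it is a further reason to grade the point as minor. It does not rescue the paragraph, which prints 0.0125 for both figures. At 0.025 the 0.685 figure would have about 86% or 99.4% power, so the two still rest on different bases. Nothing in the document says that 0.895 was obtained this way; it is only a numerical match.

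A second reply is that the method is given by citation to a textbook that was not available for this check. That is true, and the source of 0.895 cannot be ruled on. But the citation does not tell the reader which contrast is meant, and the ratios above hold for those contrasts at a common alpha whatever the source.

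Third, the 0.685 figure errs on the safe side. That is correct: for the main effects the point is one of labelling.

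**Conclusion.** The point holds and is minor. At the stated alpha, none of the definitions tried gives both figures. The figure 0.685 is a cell-versus-cell difference presented as a main effect, and it overstates the smallest detectable main effect by a factor of 0.685/0.484, about 1.41. If 0.895 means a difference of differences, its power is 72.2%, about 8 points below the claim, and the detectable effect is larger by 0.969 - 0.895 = 0.074 scale points (0.05 SD). For scale, 80% power at 0.895 would take about 105 per cell by the normal approximation. If 0.895 means half that contrast, the claim is very conservative.

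The conclusion assumes two-sided tests, effects in raw scale points, equal cells of 90 and no loss of participants. Aim 3 is exploratory and its 360 participants also serve Aims 1 and 2, so the design is unaffected.

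**What to change.** In the Aim 3 power paragraph of section 13.0:

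1. Define the main effect as the difference between marginal means (180 v 180) and the interaction as a difference of differences.
2. State that the Aim 3 tests are two-sided.
3. Keep alpha 0.0125 and 360 participants, and restate the detectable effects as 0.484 (main effect) and 0.969 (interaction).

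Alternatively, keep 0.895 and give its power as about 72%. If 0.685 is kept, label it a cell-versus-cell (simple) effect.

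If the authors intended the strictest Benjamini-Hochberg cut-off of 0.025, they should print that alpha for both figures. The interaction is then detectable at 0.894 and the main effect at half of that, 0.447.

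The cost is one definition, a statement of sidedness and two numbers. Enrolment, randomisation, outcomes and the planned analysis do not change. At alpha 0.0125 the only drawback is a slightly less favourable interaction figure.
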